12. DATA REPORTING / REGULATORY REQUIREMENTS

Adverse event lists, guidelines, and instructions for AE reporting can be found in Section 7.0 (Adverse Events: List and Reporting Requirements).

12.1 Data Reporting

12.1.1 Method

The ODQ will collect, manage, and perform quality checks on the data for this study.

12.1.2 Responsibility for Data Submission

Investigative sites within DF/HCC or DF/PCC are responsible for submitting data and/or data forms to ODQ according to the schedule set by the ODQ.

12.2 Data Safety Monitoring

The DF/HCC Data and Safety Monitoring Committee (DSMC) will review and monitor toxicity and accrual data from this study. The committee is composed of clinical specialists with experience in oncology and who have no direct relationship with the study. Information that

raises any questions about participant safety will be addressed with the Overall PI and study team.

The DSMC will review each protocol up to four times a year or more often if required to review toxicity and accrual data. Information to be provided to the committee may include: up-to-date participant accrual; current dose level information; DLT information; all grade 2 or higher unexpected adverse events that have been reported; summary of all deaths occurring within 30 days of intervention for Phase I or II protocols; for gene therapy protocols, summary of all deaths while being treated and during active follow-up; any response information; audit results, and a summary provided by the study team. Other information (e.g. scans, laboratory values) will be provided upon request.

12.3 Multicenter Guidelines

This protocol will adhere to the policies and requirements of the DF/HCC Multi-Center Data and Safety Monitoring Plan. The specific responsibilities of the Overall PI, Coordinating Center, and Participating Institutions and the procedures for auditing are presented in Appendix D.

- The Overall PI/Coordinating Center is responsible for distributing all IND Action Letters or Safety Reports to all participating institutions for submission to their individual IRBs for action as required.
- Mechanisms will be in place to ensure quality assurance, protocol compliance, and adverse event reporting at each site.
- Except in very unusual circumstances, each participating institution will order the study agent(s) directly from supplier. A participating site may order the agent(s) only after the initial IRB approval for the site has been forwarded to the Coordinating Center.

13. STATISTICAL CONSIDERATIONS

This is a non-randomized single-arm phase II study designed to evaluate the safety and efficacy of pegylated liposomal doxorubicin (PLD) and pembrolizumab for the treatment of platinum resistant recurrent ovarian, fallopian tube or peritoneal cancer. A six patient safety lead will be performed of these 2 drugs given in combination at their recommended phase II doses, respectively. If 2 out of the first 6 patients develop a DLT, the dose of PLD will be reduced to 30 mg/m². If no more than 1 patient of the first 6 patients has evidence of dose limiting toxicities, the dose level will be considered the maximum tolerated dose (MTD), an additional 20 patients will be enrolled to complete the phase II study.

13.1 Study Design/Endpoints

Primary safety endpoint:

- Dose limiting toxicity that occur during the first 4 weeks of treatment, as defined in Section 5.4

For the safety run-in using cohorts of 6 patients at any dose level, the following table gives the probability of continuing to the phase II portion of the study under varying true rates of dose-limiting toxicity.

	Acceptable dosage using 6 subjects						
True DLT rate	0.1	0.2	0.3	0.4	0.5	0.6	0.7
Probability	89%	66%	42%	23%	11%	4%	1%

Primary efficacy endpoint:

- Clinical benefit rate (CR + PR + SD \geq 24 weeks)

Secondary endpoints include:

- Toxicity by CTCAE version 4.0
- Objective response by RECIST 1.1.
- Progression-free survival
- Overall survival
- Time to progression
- Duration of response

Patients who withdraw study consent before receiving any study treatment will be replaced.

Patients who are receive study treatment, but who go off-treatment or off-study in cycle 1 and are not evaluable for DLT will be replaced for the safety run-in, but will be considered as non-responders in the final efficacy analysis.

13.2 Sample Size, Accrual Rate and Study Duration

Because of the possibility that both objective response and prolongment of progression –free intervals are enhanced when chemotherapy and immune checkpoint blockade inhibitors are combined, the primary endpoint of this study is clinical benefit rate, using an interval of at least 24 weeks of stable disease. Pujade-Lauraine et al reported a 12% objective response rate in control arm to the AURELIA of single-agent chemotherapy for platinum-resistant ovarian cancer; the probability of being progression-free at 6 months was approximately 20%.

Therefore, a true clinical benefit rate of 25% or less would not be of clinical interest, and is the null hypothesis to a binomial test for a single-stage A'Hern design. A true clinical benefit rate of 50% would be considered a clinically meaningful level of response. Sample size was chosen to have high power ($\geq 90\%$) to declare the combination effective at this rate, while controlling the one-sided Type I error at no more than 10% under the null (exact alpha = 0.091)

13.3 Interim Monitoring Plan

During the safety run-in, the first 6 patients within a dosing cohort need to complete at least one cycle of treatment, and safety data will be reviewed before enrolling additional patients.

13.4 Analysis of Primary Endpoints

Under the exact binomial test, if clinical benefit is seen at least 10 of 26 patients (38%), the null hypothesis will be rejected and the regimen will be considered worthy of further study. The observed clinical benefit rate will be reported with a two-sided 90% exact confidence interval.

13.5 Analysis of Secondary Endpoints

Treatment-related toxicities will be summarized by maximum grade and by term using CTCAE v4.0 in all patients treated at the MTD.

Best overall response will be evaluated using RECIST 1.1 and objective response requiring confirmation will be reported in all patients who receive at least one dose of treatment at the MTD.

PFS, OS, TTP and duration of response as defined in section 11.1.5 and 11.1.4, will be described using the method of Kaplan-Meier, and summarized as median PFS, OS, TTP and duration of response as well as estimates of PFS and OS at landmark time points.

All secondary endpoints will be reported with 95% confidence intervals.

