1.3 Secondary Objectives

1.3.1 To gain an estimate of toxicities for these agents when combined to treat platinum resistant recurrent ovarian, fallopian tube or peritoneal cancer

1.3.2 To gain an estimate of preliminary response rate for these agents when combined for the treatment of platinum resistant ovarian cancer, progression free survival (PFS), overall survival (OS), time to progression (TTP), and duration of response.

1.3.3 To perform exploratory translational studies on formalin fixed paraffin embedded tumor that include nanostring as well as PDL1 and exploratory immune markers.

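### If the lead-in triggers the PLD reduction, the MTD-only rule in 13.5 leaves patients treated only at the starting dose out of the one planned toxicity table

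*Combined protocol and SAP*

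**What the plan says.** The secondary objective in 1.3 is broad: "To gain an estimate of toxicities for these agents when combined" in this disease setting. The matching endpoint in 13.1 is "Toxicity by CTCAE version 4.0". Neither is restricted to a dose level.

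The analysis in 13.5 is narrower: "Treatment-related toxicities will be summarized by maximum grade and by term using CTCAE v4.0 in all patients treated at the MTD".

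Section 13 defines the MTD by the lead-in result. If no more than 1 of the first 6 patients has a DLT, "the dose level will be considered the maximum tolerated dose (MTD), an additional 20 patients will be enrolled to complete the phase II study". If 2 of the first 6 have a DLT, PLD goes from 40 to 30 mg/m² (also in 5.1 and 5.4). Section 13.1 foresees more than one level: "For the safety run-in using cohorts of 6 patients at any dose level". It adds that treated patients who leave in cycle 1 and are "not evaluable for DLT will be replaced for the safety run-in". Under 13.3, "the first 6 patients within a dosing cohort need to complete at least one cycle of treatment", and safety data are reviewed before more patients enter.

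DLT in the first four weeks is listed in 13.1 as the primary safety endpoint. Section 13.4 describes only the clinical benefit analysis and gives no analysis for DLT.

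**The concern.** Read together, these rules make the toxicity population depend on the toxicity result. If the starting level passes, its lead-in patients are in the table. If it fails, it is not the MTD, and patients who received only that dose are not in the table. The omission can therefore occur only in the branch where toxicity changed the dose, and it removes the cohort that prompted the change.

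At stake is the completeness of the toxicity estimate promised in 1.3. DLTs cover cycle 1 only and are defined narrowly in 5.4. The starting-dose cohort's other treatment-related toxicity, including anything after cycle 1, would have no planned tabulation. A table added after a reduction had occurred would be a post hoc choice.

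**Working it through.** **Inputs.** Cohort size 6 and the grid of true DLT rates (13.1); MTD rule of at most 1 DLT in 6 and reduction trigger of 2 in 6 (13; trigger also in 5.1 and 5.4); 20 further patients (13); total enrolment goal 26 (front sheet, item 5). The documents give no expected DLT rate for the combination, so 10%, 20% and 30% are taken from the 13.1 grid as a range.

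**Step 1: reproduce the plan's table.** With X ~ Bin(6, p), P(X ≤ 1) = (1−p)⁶ + 6p(1−p)⁵.
- p = 0.1: 0.5314 + 0.3543 = 0.8857 (plan: 89%)
- p = 0.2: 0.2621 + 0.3932 = 0.6554 (plan: 66%)
- p = 0.3: 0.1176 + 0.3025 = 0.4202 (plan: 42%)

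The other four columns of the 13.1 table also reproduce.

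**Step 2: chance of the affected branch.** The text says 2 DLTs. It does not say what follows 3 or more, although only 0 or 1 allows continuation. Both readings are shown, with P(X = 2) = 15p²(1−p)⁴ and P(X ≥ 2) = 1 − P(X ≤ 1).

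| True DLT rate | Exactly 2 (literal trigger) | 3 or more | 2 or more (assumes 3+ also leads to a reduction) |
|---|---|---|---|
| 10% | 9.8% | 1.6% | 11.4% |
| 20% | 24.6% | 9.9% | 34.5% |
| 30% | 32.4% | 25.6% | 58.0% |

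**Step 3: share of treated patients left out.** The documents do not state the total treated after a reduction, so two totals are assumed.
- Enrolment held at 26: 6/26 = 23%.
- A new cohort of 6 plus 20 more, giving 6 + 6 + 20 = 32: 6/32 = 19%.
- One run-in patient replaced, total 26: 7/26 = 27%. The 23% is therefore not an upper bound.
- Lead-in patients who move to the reduced dose and are counted as treated at the MTD: lower than these figures, by an amount the plan does not fix.

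The last case arises in two ways. Sections 5.1, 5.4 and 13 do not say whether the reduction applies to lead-in patients still on PLD. Separately, an individual 25% cut under 6.1 takes a 40 mg/m² patient to 40 × 0.75 = 30 mg/m², the reduced level. Section 13.5 does not say whether either patient counts.

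**Step 4: illustration.** Take a treatment-related term that is not a DLT, for example one arising after cycle 1. Suppose it is seen in 2 of 6 patients treated only at the starting dose and in nobody at the reduced dose. Exact (Clopper-Pearson) 95% intervals:

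| Summary | Count | Rate (95% CI) |
|---|---|---|
| Starting dose | 2/6 | 33% (4–78%) |
| All treated, total 26 | 2/26 | 7.7% (1–25%) |
| All treated, total 32 | 2/32 | 6.3% (1–21%) |
| MTD only, total 26 | 0/20 | 0% (0–17%) |
| MTD only, total 32 | 0/26 | 0% (0–13%) |

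The planned table would show no event for a term that occurred in two treated patients.

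**Step 5: is there another planned summary?** Section 13.3 is a review before further enrolment. Section 12.2 is committee monitoring of toxicity and accrual. Section 7.6 is case-level reporting on the toxicity forms. Section 13.4 covers efficacy only. None specifies a reported toxicity summary that includes the starting-dose cohort.

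**The case against.** The strongest reply is that nothing is lost. Adverse events are recorded for everyone (7.6), toxicity is monitored (12.2), and the lead-in data are reviewed before enrolment continues (13.3). An MTD-only table is a legitimate estimate for the dose carried forward, and 13.5 does not forbid another column. All of this stands and keeps the point minor. It does not supply the missing planned summary: the MTD-only table is the only one specified, for an objective with no dose limit.

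A second reply is that the exclusion is not certain. The branch may not occur, and lead-in patients who move to the reduced dose could be read as treated at the MTD. Both are correct. The conclusion is therefore limited to patients treated only at the starting dose, after a reduction.

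A reader might also infer that the DLTs behind a reduction would go unreported. The documents do not support that. DLT is a separate primary safety endpoint, the count decides the dose, and Section 14 promises a full report of the outcomes. What is true is narrower: 13.4 gives no analysis for DLT, and Section 14 is a publication commitment rather than an analysis rule.

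**Conclusion.** The concern holds in a conditional form. If the lead-in triggers the PLD reduction, the rule in 13.5 leaves patients treated only at the starting dose out of the only toxicity summary specified by grade and term, although the objective and endpoint are not limited to the MTD.

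Across true DLT rates of 10% to 30%, the branch has probability 10% to 32% on the literal trigger. It is 11% to 58% if 3 or more DLTs also lead to a reduction, which is an assumption. For a six-patient cohort the omission is 19% to 23% of treated patients under the two assumed totals. Replacement can raise this, and counting patients who switch dose can lower it. With at most 1 DLT in the first 6, there is no issue.

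It would go too far to infer that safety data are lost or that the trial's safety decisions are affected: collection, monitoring and the lead-in review cover every treated patient. Severity: minor.

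**What to change.** In 13.5, specify that treatment-related toxicities are summarized by maximum grade and term in all treated patients, by PLD starting dose and overall, with the MTD group kept as one column. Assign patients to the dose columns by starting dose, so that a later move to the reduced level, whether cohort-wide or individual, does not shift them between columns. State in the same sentence how patients who change level are handled in the MTD column.

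The cost is one extra split of the toxicity table. Enrolment, data collection and the lead-in rule do not change. If the first cohort passes, the all-treated and MTD columns coincide.

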7.6 Routine Adverse Event Reporting

All Adverse Events **must** be reported in routine study data submissions to the Overall PI on the toxicity case report forms. **AEs reported through expedited processes (e.g., reported to the IRB, FDA, etc.) must also be reported in routine study data submissions.**

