1. OVERVIEW

The purpose of this document is to provide study sites with guidance on the identification and management of Events of Clinical Interest for the MK-3475 (also known as pembrolizumab) program.

Based on the literature review [1-11], and consideration of mechanism of action of pembrolizumab, potential immune-related adverse events (irAEs) are the primary Event of Clinical Interest (ECI). Immune-related AEs are adverse events associated with the treatment of patients with immunotherapy treatments that appear to be associated with the immune therapy's mechanism of action. Based on these potential irAEs, the sponsor has defined a list of specific adverse event terms (ECIs) that are selected adverse experiences that **must be reported to Merck within 24 hours to Merck Global Safety (Attn: Worldwide Product Safety; [contact])** from the time the Investigator/physician is aware of such an occurrence, regardless of whether or not the investigator/physician considers the event to be related to study drug(s). In addition, these ECIs require additional detailed information to be collected and entered in the study database. ECIs may be identified through spontaneous patient report and / or upon review of subject data. **Table 1** provides the list of terms and reporting requirements for AEs that must be reported as ECIs for MK-3475 protocols. Of note, the requirement for reporting of ECIs applies to all arms, including comparators, of MK-3475 clinical trials.

Given that our current list of events of clinical interest is not comprehensive for all potential immune-related events, it is possible that AEs other than those listed in this document may be observed in patients receiving pembrolizumab. Therefore any Grade 3 or higher event that the investigator/physician considers to be immune-related should be reported as an ECI regardless of whether the specific event term is in **Table 1 and reported to Merck within 24 hours to Merck Global Safety (Attn: Worldwide Product Safety; [contact])** from the time the Investigator/physician is aware of such an occurrence. Adverse events that are both an SAE and an ECI should be reported one time as an SAE only, however the event must be appropriately identified as an ECI as well in the database.

Table 1: Events of Clinical Interest

Pneumonitis (reported as ECI if \geq Grade 2)		
Acute interstitial pneumonitis	Interstitial lung disease	Pneumonitis

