2. ECI REPORTING GUIDELINES

ECIs are selected non-serious and serious adverse experiences that must be reported to Merck within 24 hours regardless of attribution to study treatment. The AEs listed in this document and any event that meets the ECI criteria (as noted) in Table 1 or in the respective protocol (event term and Grade) must be reported regardless of physician-determined causality with study medication and whether or not considered immune-related by the physician (unless otherwise specified). Physicians/study coordinators/designated site personnel are required to record these experiences as ECIs on the Adverse Experience electronic Case Report Forms (eCRFs) (or on paper) and to provide supplemental information (such as medical history, concomitant medications, investigations, etc.) about the event.

- Please refer to the Data Entry Guidelines (DEGs) for your protocol (Section 12.1).
- Please refer to protocol for details on reporting timelines and reporting of Overdose and Drug Induced Liver Injury (DILI) (Section 7.0).

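### The only planned toxicity table is limited to treatment-related events, although the toxicity objective, endpoint and data collection carry no attribution limit

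*Combined protocol and SAP*

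**What the plan says.** Section 13.5 gives the toxicity analysis in one sentence: "Treatment-related toxicities will be summarized by maximum grade and by term using CTCAE v4.0", for patients treated at the MTD. Section 13 has no table of adverse events of any cause and no summary of ECIs, SAEs or deaths.

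The objective and endpoint that this sentence serves are wider. Objective 1.3.1 is "To gain an estimate of toxicities for these agents when combined", and section 13.1 lists the endpoint as "Toxicity by CTCAE version 4.0".

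Collection is also wider. Section 7.6 requires all adverse events to "be reported in routine study data submissions to the Overall PI on the toxicity case report forms". Appendix B, section 2, says that events meeting the ECI criteria "must be reported regardless of physician-determined causality with study medication and whether or not considered immune-related by the physician". The paragraphs after Table 1 in Appendix B keep that reporting duty even when evaluation finds the event not to be related.

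Attribution rests with the investigator (section 6) on a five-level scale (section 7.2): definite, probable, possible, unlikely, unrelated. Section 13.5 does not say which levels count as treatment-related. The other toxicity measure, DLT (section 5.4), covers cycle 1 only and counts only events that the treating physician relates to study treatment.

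**The concern.** The plan collects without regard to cause and then analyses by cause, so the analysis is narrower than the endpoint that it is meant to deliver.

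This matters because the disease can mimic some of the events of interest. The ECI list in Appendix B includes intestinal obstruction, gastrointestinal perforation and transaminase elevations. The protocol itself treats bowel obstruction as a problem of this population (it becomes an exclusion after the run-in, 3.2.21.1), and it allows higher AST and ALT at entry with liver metastases (Table 1 in 3.1.10). For such an event the physician must choose between drug and cancer, and there is no control arm against which to check the choice. With only the related table published, a reader could not see how many events attribution had removed. An early trial of a new combination is where that information is most useful.

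**Working it through.** **1. The plan's own figures.** The plan states no number on this point. The neighbouring figures reproduce:

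- Efficacy rule, at least 10 of 26: P(X ≥ 10 | n = 26, p = 0.25) = 0.0909 (stated 0.091), and P(X ≥ 10 | n = 26, p = 0.50) = 0.916 (stated at least 90%).
- DLT table, P(X ≤ 1 | n = 6, p) for p = 0.1 to 0.7: 88.6, 65.5, 42.0, 23.3, 10.9, 4.1 and 1.1% (stated 89, 66, 42, 23, 11, 4 and 1%).

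None of these uses the toxicity table, so nothing here changes them.

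**2. The provisions side by side.**

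| Place | Role | Limited by attribution? |
|---|---|---|
| 1.3.1 | Toxicity objective | No |
| 13.1 | Toxicity endpoint | No |
| 7.6 | Collection of adverse events | No |
| Appendix B, sections 1 and 2 | ECI reporting | No |
| 5.4 | DLT (cycle 1) | Yes |
| 13.5 | Toxicity analysis | Yes, levels undefined |

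The limit appears only in the two places where toxicity is counted. An event judged unrelated is therefore in the data and in neither specified measure.

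**3. What one patient is worth.** With the planned N = 26 all treated at the MTD, 1/26 = 3.8 percentage points.

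**4. Illustration (the counts are assumptions).** Suppose 5 patients have an ECI of any cause: 5/26 = 19.2% (exact 95% CI 6.6 to 39.4%). If 2 of the 5 are judged unrelated, the related table shows 3/26 = 11.5% (2.4 to 30.2%).

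**5. Range (the rates are assumptions).** Let q be the proportion of patients with an ECI of any cause, and m the proportion of those whose event is judged unrelated. The expected number missing is 26 × q × m. The chance that at least one is missing is 1 − (1 − qm)^26, taking patients as independent.

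- q = 10%, m = 10%: 26 × 0.01 = 0.26 patients; 1 − 0.99^26 = 23%.
- q = 20%, m = 25%: 26 × 0.05 = 1.3 patients; 1 − 0.95^26 = 73.6%.
- q = 30%, m = 50%: 26 × 0.15 = 3.9 patients; 1 − 0.85^26 = 98.5%.

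These figures measure the gap between the all-cause and related tables. They do not measure error against the true drug-caused rate: if the 2 omitted patients in step 4 really had disease-caused events, 11.5% is the right drug-related figure.

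**The case against.** The strongest reply is that the objective concerns the toxicity of the agents, so a related-only table aims at the right quantity. Possible is a low bar on the section 7.2 scale; if it counts, most uncertain events stay in. An all-cause table in a single-arm trial cannot separate drug from disease either. Safety oversight does not depend on this table: all adverse events are collected, ECIs go to the manufacturer within 24 hours whatever their cause, and the material that the DSMC may receive (12.2) carries no stated attribution filter.

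Much of this stands. It shows that neither table is enough alone, which is a reason to present both. It does not reconcile 13.5 with an endpoint that has no attribution limit, and monitoring is not the trial's reported estimate. Whether possible counts is exactly what 13.5 leaves open.

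Three inferences that a reader might add are not supported:

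- That the overlapping toxicities of the two drugs remove events from the table. Section 7.2 attributes to study treatment as a whole, so an event that could come from either drug is still related.
- That Appendix B pushes uncertain events towards unrelated. It asks sites to try to rule out other causes, but sets no such default. For suspected pneumonitis, management follows the guidance until a treatment-related cause is excluded.
- That confirmed immune events are being dropped. ECIs are a list of terms, reportable whether or not the physician thinks them immune-related.

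**Conclusion.** The point holds as a mismatch between the endpoint and its analysis. As written, events judged unrelated enter no specified toxicity analysis, though they remain in the database and can be tabulated.

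A reader might conclude that the related-only table can only understate toxicity. That is true against all-cause incidence. Against true drug-caused incidence, attribution can err either way: drug events may be called unrelated, and disease events may be called related. The documents do not show which error prevails.

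The size cannot be derived from the documents, which give no attribution rate. What can be said is 3.8 percentage points per omitted patient if all 26 are treated at the MTD. Under the assumed ranges above, the expected number missing from the related table runs from about 0.3 to 3.9 patients. This should be corrected, but it does not threaten the efficacy conclusion: the test, alpha, power and the DLT rule do not depend on it.

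**What to change.** In section 13.5:

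1. Add a table of all adverse events regardless of attribution, by maximum grade and term, with ECIs, SAEs and deaths on the same basis.
2. Keep the treatment-related table beside it, and define treatment-related as possible, probable or definite. This matches the grouping already used in the reporting table of section 7.3.3.

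The cost is additional tabulation from data that the protocol already collects, with no new procedures and no change to sample size or to any clinical rule. The downside is that the all-cause rates will include disease-related events and look higher. The text should say so and direct the reader to both tables.
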